6.2.2 Analysis of secondary efficacy variables

6.2.2.1 Secondary efficacy variables: primary analysis

Secondary efficacy variables are as follows:

- Time to first occurrence of the following CV composite endpoint: cardiovascular (CV) death or non-fatal CV events (i.e. myocardial infarction, stroke, or hospitalization for HF)
- Time to all-cause mortality

- Time to all-cause hospitalization
- Change in UACR from baseline to Month 4
- Time to first occurrence of the following renal composite endpoint: onset of kidney failure, a sustained decrease in eGFR of $\geq 57\%$ from baseline over at least 4 weeks or renal death.

The primary analysis of the secondary efficacy variables will be conducted in the FAS.

See section 4.7 for the testing hierarchy for secondary endpoints and for multiplicity adjustment of significance levels.

The primary analysis of the secondary time-to-event endpoints will be conducted analogously to the primary analysis of the primary composite endpoint, with modifications to the censoring rules as the events will differ. In the event of premature termination from the study with no subsequent follow-up information, subjects without any information about the composite endpoint after baseline will be censored at Day 1, and the following censoring rules will also apply:

- CV events will be counted up to the day of withdrawal from the study or non-CV death. Randomized subjects without an event of the CV composite endpoint at the time of analysis will be censored at the date of their last contact up to and including the EOS visit or date of non-CV death.
- Hospitalization events will be counted up to the day of withdrawal from the study or death. Randomized subjects without a hospitalization event at the time of analysis will be censored at the date of their last contact up to and including the EOS visit or date of death.
- All-cause mortality will be counted up to the last date vital status could be obtained. Randomized subjects without such an event at the time of analysis will be censored at the last date vital status could be obtained up to and including the EOS visit.

An ANCOVA model will be fitted to the logarithmized ratios of UACR at Month 4 to UACR at baseline including the factors treatment group, the stratification factors region, type of albuminuria and eGFR category and the logarithmized baseline UACR as covariate. Corresponding two-sided 95% confidence intervals will be computed. As the baseline UACR defines the type of albuminuria, the log-transformed baseline UACR will be nested as covariate in type of albuminuria.

6.2.2.2 Secondary efficacy variables: supportive analysis

The primary analysis of the secondary efficacy time-to-event endpoints will be repeated in the PPS as a supportive analysis. For the PPS analysis, the censoring rules for the secondary analysis specified in Section 6.2.2.1 will be further restricted to events occurring up to 30 days after last study drug intake.

Accordingly, subjects with censoring or event date more than 30 days after last study drug intake in the primary analysis will be censored at the date of last study drug intake +30 days.

The supportive analyses of the secondary time-to-event endpoints will correspond to those done for the primary composite endpoint in the FAS and PPS (see section 6.2.1.2), except for the ‘on-treatment’ and tipping point analysis which will only be performed for the key secondary endpoint based on the FAS.

UACR at Month 4 in the PPS will be analyzed using an ANCOVA as described above. In addition, the following sensitivity analyses accounting for missing data at Month 4 will be conducted:

- On-treatment LOCF approach, only including data up to 30 days after stop of study medication (FAS and PPS).
- Baseline observation carried forward analysis (BOCF), imputing the baseline value for missing data and thus including all subjects with missing Month 4 data with a value of 1 for the ratio of UACR baseline to Month 4 (FAS).
- Multiple imputation analysis (FAS): For reproducibility, the SAS seed number for creating the random numbers will be set to the study (16244). Further details are given in section 9.2.

For all PPS analyses of UACR at month 4, only data up to 30 days after stop of treatment will be considered, all other data will be set to missing before employing the above-mentioned imputation techniques.

6.2.3 Analysis of other exploratory efficacy variables

Other exploratory efficacy variables will be as follows:

- Time to onset of kidney failure
- Time to onset of ESRD
- Time to onset of eGFR decrease to less than 15 mL/min/1.73 m² sustained over at least 4 weeks
- Time to onset of eGFR decrease of $\geq 40\%$ sustained over at least 4 weeks
- Time to onset of eGFR decrease of $\geq 57\%$ sustained over at least 4 weeks
- Time to CV death
- Time to non-CV, non-renal death
- Time to first CV hospitalization (either hospitalization for HF, other cardiovascular hospitalization or adjudicated CV event associated with hospitalization)
 - Causes for other cardiovascular hospitalizations include unstable angina, arrhythmia, and peripheral arterial disease.
 - CV events associated with hospitalization include (if not already considered as “other cardiovascular hospitalization”) CV death, new onset of atrial fibrillation/flutter, non-fatal myocardial infarction, non-fatal stroke and transient ischemic attack.
- Time to first hospitalization for HF
- Time to first non-fatal stroke
- Time to first non-fatal myocardial infarction
- Time to first occurrence of the composite endpoint of CV death, non-fatal stroke or non-fatal myocardial infarction
- Time to first occurrence of the composite endpoint of CV death or hospitalization for HF

- Time to first occurrence of the composite endpoint of CV death, kidney failure, eGFR decrease of $\geq 57\%$ sustained over at least 4 weeks or renal death
- Number of subjects with new diagnosis of atrial fibrillation or atrial flutter
- Number of subjects with new diagnosis of HF
- Change in UACR from baseline
- Change in eGFR from baseline
- Regression from very high to high albuminuria and high albuminuria to normalalbuminuria accompanied by a decrease in UACR of at least 30% from baseline
- Number of subjects with UACR decrease of at least 30% from baseline at any time post-baseline
- Number of subjects with UACR decrease of at least 50% from baseline at any time post-baseline
- Change in QoL summary scores measured by the following health-related quality of life (HRQoL) questionnaires: Kidney Disease Quality of Life (KDQOL 36) and EuroQol Group 5 dimension, 5 level questionnaire (EQ 5D 5L)

All these other efficacy variables will be analyzed in FAS and PPS (as applicable) in an explorative manner. For all PPS analyses, only data points and events up to 30 days after stop of study drug will be considered.

6.2.3.1 Components of primary and secondary composite endpoints

Consistent with the methods for the primary and secondary efficacy variables, components or composites of the components of the primary and secondary time-to-event endpoints (as included in the list of other exploratory efficacy variables above) will be analyzed as exploratory time-to-event variables using the stratified logrank test stratified by the stratification factors. A point estimate of the hazard ratio and a corresponding two-sided 95% confidence interval will be calculated using a stratified Cox proportional hazard regression model. Kaplan Meier curves will be provided for the cumulative proportions of events by treatment groups.

6.2.3.2 UACR and albuminuria

UACR during the study will be summarized descriptively by treatment group and visit including ratios to baseline. These analyses will be performed overall and separated by the stratification factors (region, type of albuminuria at screening and eGFR category at screening).

The log-transformed ratio of UACR to baseline at each visit up to the last visit with a reasonable number of subjects with UACR measurements will be analyzed by a mixed model repeated measures (MMRM) with the factors treatment group, visit, treatment-by-visit interaction, factors for the stratification levels, log-transformed baseline value as covariate nested within type of albuminuria and log-transformed baseline value by visit interaction. Pairwise ratios between the finerenone and the placebo treatment group will be calculated and corresponding two-sided 95% confidence intervals will be computed.

An on-treatment analysis including measurements restricted to up to 30 days after last intake of study drug will be performed using the same model as above. The SAS procedure PROC

MIXED will be used estimating covariance patterns within subjects to adjust for the within subject variance. For each treatment group a separate covariance pattern will be estimated based on an unstructured covariance. In case of convergency issues, an alternative covariance matrix will be used, with Toeplitz matrix as first choice alternative.

Frequency tables will be generated for the number of subjects with a relative decrease and increase in UACR of $\geq 30\%$, $\geq 40\%$ and $\geq 50\%$ from baseline UACR. The analysis will be performed for each visit and for any time post baseline. The analysis will also be performed stratified for each level of the stratification factors.

A shift table will be provided displaying the number of subjects who changed from baseline to each visit from very high albuminuria to high albuminuria, from very high albuminuria to normalalbuminuria (UACR $< 30\text{mg/g}$), from high albuminuria to normalalbuminuria (UACR $< 30\text{mg/g}$), from high albuminuria to very high albuminuria and from normalalbuminuria (UACR $< 30\text{mg/g}$) to high and very high albuminuria by treatment group and overall. The albuminuria category changes will only be considered as shifts if they are accompanied by a UACR decrease or increase of at least 30% from baseline to each visit.

The additional categorical UACR efficacy variables will be summarized for presence or absence of the event using logistic regression with the factors treatment group and stratification levels. Pairwise differences between the finerenone and the placebo treatment group will be calculated and corresponding two-sided 95% confidence intervals will be computed.

6.2.3.3 Decrease in eGFR

eGFR will be summarized descriptively by treatment group and visit including absolute and relative changes to baseline. These analyses will be performed overall and separated by the stratification factors.

The absolute change of eGFR to baseline at each visit until the last visit with a reasonable number of subjects with eGFR measurements will be analyzed by a mixed model with the factors treatment group, visit, treatment-by-visit interaction, factors for the stratification levels, baseline value as covariate (nested within eGFR category) and baseline by visit interaction. Pairwise differences between the finerenone and the placebo treatment group will be calculated and corresponding two-sided 95% confidence intervals will be computed.

An on-treatment analysis including measurements restricted to up to 30 days after last intake of study drug will be performed using the same model as above.

The SAS Procedure PROC MIXED will be used estimating covariance patterns within subjects to adjust for the within subject variance. For each treatment group a separate covariance pattern will be estimated based on an unstructured covariance.

Frequency tables will be generated for the number of subjects with a relative decrease in eGFR of $\geq 30\%$, $\geq 40\%$, $\geq 50\%$ and $\geq 57\%$ from baseline eGFR. The analysis will be performed for each visit and for any time post baseline.

For each patient with 1 or more post-baseline eGFR measurements, the annualized change in eGFR will be calculated by fitting the patient's eGFR assessments into a linear regression model with time in years as the independent variable. The derived annualized change will be analyzed using an ANCOVA model including baseline, treatment group and stratification factors as fixed-effects.

The following additional analysis of acute and chronic eGFR slopes will be performed.

- Change in eGFR from baseline (Visit 1) to the PD or EOS Visit
- Acute eGFR changes from baseline to Month 4
- Change in eGFR from Month 4 to the PD or EOS Visit
- Correlation analyses between short term eGFR changes between baseline and Month 4 after randomization, and long term eGFR decline (chronic slope).

An ANCOVA model will be fitted to the eGFR efficacy variables including the factors treatment group, the stratification factors and the baseline eGFR as covariate. Corresponding two-sided 95% confidence intervals will be computed. In addition, correlation analyses between short term eGFR changes between baseline and Month 4 after randomization, and long term eGFR decline (chronic slope) will be performed.

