9.7.8.1.3 Iohexol clearance sub-study - amended

This section was changed in Amendment 3, see Section [15.1.2.35](#).

At selected centers in Italy, at least 50 subjects per study consenting to participate in Studies 16244 and 17530 will be invited to take part in an iohexol clearance sub-study. Subjects will be asked to sign a separate informed consent to participate in this sub-study.

Subjects who are included in this sub-study will have their GFR directly measured by the iohexol plasma clearance technique (44).

Iohexol plasma clearance will be assessed at Visit 1 (Day 1, baseline), at Visit 3 (Month 4) and thereafter at every other visit (i.e. every 8 months) until the end of the study (either at the PD Visit or the EOS Visit) plus an additional assessment at the PT Visit (recovery). The Iohexol results will not be provided to the sites.

The variables for evaluation in this sub-study are as follows:

- Primary variable:
Chronic GFR slope, i.e. the rate of GFR decline from Visit 3 (Month 4) after randomization to the end of the treatment period.

As previously addressed in the AASK trial, this approach is needed to address the biphasic change in GFR decline that is expected after exposure to the study drug. The GFR slope will be determined separately during the first 4 months following randomization (acute slope) and after 4 months (chronic slope). The acute and chronic phases are differentiated because the study treatment might have acute effects on GFR that may differ from its long term effects on disease progression (45, 46) (an approach approved by the U.S. National Institute of Diabetes and Digestive and Kidney Diseases (47)).
- Exploratory variable:
 - Change in GFR from Visit 1 (baseline) and at the PT Visit (recovery)
 - Acute GFR changes from baseline to Visit 3 (Month 4)
 - Acute GFR changes from the end of the treatment period until the end of the recovery period
 - Correlation analyses between short term GFR changes between Visit 1 (baseline) and Visit 3 (Month 4) after randomization, and long term GFR decline (chronic slope).

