where SD_{ln} is the standard deviation of the 3 log-transformed UACR values. If the coefficient of variation exceeds 25%, the median from the measurements will be used for the analyses. The median in case of an even number of values will be defined as the geometric mean from the 2 middle values. If the coefficient of variation is 25% at the most, the geometric mean will be used. If 2 or 3 scheduled assessments are missing or invalid and unscheduled assessments have been performed, then the set of unscheduled measurements closest to the planned visit will be used to determine the UACR at the respective visit if performed within 30 days before or after the planned time point for all visits from Visit 3 (Month 4) onwards (with the following exception: only samples with 2/3 of values no later than 30 days (for “last on-treatment” analysis) or 3 days (for “last treatment-emergent” analysis) after last study drug intake will be considered). For Visit 1, 2 out of 3 samples have to be on or before the day of randomization and have to lead to non-missing values in order for the set of samples to be valid for baseline calculation; otherwise (also including the case when there is one valid sample at Visit 1), the set of screening samples will be considered for baseline.

In the case of ESRD, the UACR and eGFR values after the onset date of ESRD will be excluded from all efficacy analyses, but included in the safety analyses.

For the stratification group type of albuminuria at screening (high or very high), the classification supplied from the central lab via IxRS will be used. The rule that has been applied by the central lab for this classification is, if there are 3 values, the median value should be taken; if 2 values, then the arithmetic mean value, regardless of degree of variation between the values. The lab reports from the run-in and screening visits will include the type of albuminuria, to assist the investigators in reducing stratification and randomization errors.

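### The SAP's chronic-phase eGFR item is an unscaled change over unequal intervals, so it does not estimate the chronic slope that the section announces

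*SAP*

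**What the plan says.** SAP 6.2.3.3 introduces the block with "The following additional analysis of acute and chronic eGFR slopes will be performed". It then lists three changes (baseline to PD or EOS, baseline to Month 4, and "Change in eGFR from Month 4 to the PD or EOS Visit") and a correlation of the early change with the long-term decline. The correlation item uses the term chronic slope but does not define it.

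The model sentence reads "An ANCOVA model will be fitted to the eGFR efficacy variables including the factors treatment group", and adds the stratification factors and baseline eGFR. Neither the variable nor the model contains elapsed time. SAP 4.5.2, written for change from baseline, treats an absolute change as a simple difference.

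Two other analyses in 6.2.3.3 are relevant:
- a per-patient regression, described as a "linear regression model with time in years as the independent variable", with no Month 4 start;
- a mixed model for the change from baseline at each visit, with a treatment-by-visit term and an on-treatment repeat.

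Protocol 9.7.8.1.3 does define a chronic slope, as "the rate of GFR decline from Visit 3 (Month 4) after randomization to the end of the treatment period", but for measured GFR in the iohexol sub-study.

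On missing values, SAP 4.5.3 says that "the UACR and eGFR values after the onset date of ESRD will be excluded from all efficacy analyses". Protocol 9.2.9 waives the PD Visit if it cannot take place within 7 days of permanent stop. Protocol 6.4.1.1 and 11.4 expect patients who stop drug to keep attending visits.

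**The concern.** Acute and chronic phases are separated so that an early, possibly reversible drop in eGFR is not confused with the slower loss that follows. That needs a rate for the second phase. A difference between two values, taken over whatever time a patient happened to be followed, mixes the rate of decline with the length of the interval.

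Three consequences follow. The result has no per-year reading and cannot be compared with other slope estimates. Interval length adds noise unrelated to treatment, and for this item the central eGFR values between the two end points go unused. If interval length differs by arm, part of that difference appears as a treatment effect.

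The SAP also leaves open which value is used when a patient has both a PD and an EOS Visit, what happens when the PD Visit falls before Month 4, and what is done for a patient with no usable value before death or ESRD.

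**Working it through.** **Inputs from the plan.** SAP section 3: accrual 33 months, last patient treated 11 months, total 44 months, 4690 subjects, 1068 events. Protocol 10.4: finerenone discontinuation 5% per year; no placebo discontinuation rate is given. The slope analysis has no sample size or power of its own.

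**Timeline check.** 33 + 11 = 44. A log-rank calculation with uniform accrual on this timeline (hazard ratio 0.80, placebo hazard −ln(0.88), 0.7% per year lost to follow-up, 5% per year stopping finerenone and reverting to the placebo hazard) gives 1068 to 1069 events and 89.9 to 90.0% power at 4690 subjects. The timeline is therefore the one behind the plan's own figures.

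**Interval from Month 4 to EOS.** Longest: 44 − 4 = 40 months. Shortest: 11 − 4 = 7 months. Ratio: 40 / 7 = 5.7.

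**If PD values are used.** A simulation with uniform accrual and exponential stopping at 5% per year (no deaths, ESRD or loss to follow-up) gives:
- about 11% of patients stop before EOS;
- 1 − 0.95^(4/12) = 1.7% stop before Month 4, where the interval is negative;
- positive intervals run from about 0 to 40 months, with 5th, 50th and 95th percentiles of 7.6, 21.9 and 38.0, mean 22.2 and coefficient of variation about 45%.

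**Same rate, different outcome.** Change = rate × months / 12, at an assumed −3 mL/min/1.73 m² per year:

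| Interval (months) | Raw change | Change per year |
|---|---|---|
| 1 | −0.25 | −3.0 |
| 7 | −1.75 | −3.0 |
| 20 | −5.0 | −3.0 |
| 40 | −10.0 | −3.0 |

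**Noise from interval length.** SD of the interval = 0.447 × 22.17 = 9.9 months = 0.83 years. At assumed declines of 2 to 4 per year this alone contributes an SD of 0.83 × 2 = 1.7 to 0.83 × 4 = 3.3 mL/min/1.73 m² between patients who share one true rate.

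**Spurious difference with equal true slopes.** Difference (finerenone minus placebo) = rate × difference in mean interval in years, using the PD value for everyone who stops and keeping positive intervals only. Decline rates, the placebo stopping rate and the higher finerenone rates are assumptions.

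| Assumed decline per year, both arms | Stopping 5% v 5% | 8% v 5% | 10% v 5% |
|---|---|---|---|
| 2 | 0.00 | 0.12 | 0.21 |
| 3 | 0.00 | 0.19 | 0.32 |
| 4 | 0.00 | 0.27 | 0.44 |

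Hand check of the last cell: mean intervals are 22.17 months (5%) and 20.92 months (10%); (22.17 − 20.92) / 12 × 4 = 0.42, which agrees within simulation error. After dividing by time, every cell is 0.

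**Scale when there is a true effect.** With assumed rates of −3 v −4 per year, the raw difference is 1.85 at 5% stopping in both arms, which is 1.0 × 22.17 / 12. It becomes 2.15 at 10% v 5%. A reader given 1.85 or 2.15 could not recover the 1.0 per year.

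**The case against.** The strongest reply is that little depends on this item. SAP 6.2.3 lists eGFR change as exploratory, and SAP 4.7 keeps it out of the testing hierarchy. The by-visit mixed model already compares the arms at common times, at Month 4 and later, so an acute drop would be visible without this item. The correlation item names a chronic slope, so a rate may have been meant. All of this stands and limits the priority. It does not supply the rate: the by-visit model specifies no contrast between Month 4 and later visits and no slope, and the annualized regression blends the acute and chronic phases.

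Four stronger readings are tempting, and the documents do not support them:

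- **That the comparison is biased towards finerenone.** Randomization balances entry dates. Bias through stopping needs both the PD value to be used and unequal stopping rates. The SAP fixes neither. If EOS is taken whenever it exists, patients who stop and stay in follow-up keep their full interval; both the bias and the negative intervals then largely disappear, at the price of including off-drug time. Hyperkalaemia is an identified risk (Protocol 3.3), so unequal stopping is plausible, but it is not a plan figure.
- **That patients who die or reach ESRD are dropped.** No text says so. SAP 4.5.3 removes only values after ESRD onset, and a PD value between Month 4 and that point still counts. What is missing is a rule for patients with no such value.
- **That the section contains no slope at all.** It contains an annualized one; it is not the chronic one.
- **That the protocol defines the main-study chronic slope as a rate.** That definition belongs to the sub-study. The main-study eGFR section (Protocol 10.3.3.5.2) plans no chronic slope.

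**Conclusion.** The concern holds as a mismatch between what SAP 6.2.3.3 announces and what it specifies. Followed as written, the chronic-phase item yields a raw change over 7 to 40 months at EOS, and less at PD, that is not a rate.

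The certain harm is an estimate without a per-year meaning, with avoidable variance. Bias is conditional: about 0.1 to 0.4 mL/min/1.73 m² under the assumed declines and unequal stopping above, and zero if stopping is equal. The intervals rest on the planned timeline. The trial is event-driven, and SAP section 3 reports a slower event rate and an increase to about 5800 subjects, so the actual range may differ; unequal follow-up remains under staggered entry with a common end of study.

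Priority is low to moderate because the analysis is exploratory.

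**What to change.** In SAP 6.2.3.3:

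- Define the chronic slope as an annualised rate of eGFR change from Month 4. One suitable form is a linear mixed model with random intercept and slope, treatment-by-time, stratification factors and baseline eGFR, on all scheduled central eGFR values from Month 4. The minimum is a per-patient regression slope starting at Month 4.
- Use the same definition in the correlation item.
- State whether values after permanent stop of study drug are included. This replaces the unresolved choice between PD and EOS and settles PD Visits before Month 4.
- Keep the exclusion of values after ESRD onset from SAP 4.5.3, and state that patients who die or reach ESRD contribute their values up to that point.

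The cost is SAP wording and one extra model. Central eGFR is already collected every 4 months (Protocol Table 9-1), so no new data are needed. The downside is an assumption of linear decline after Month 4, which the term slope already implies.
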